Official Title: EngagINg the COmmunity to Reduce Preterm Birth Via
Adherence To an Individualized Prematurity Prevention Plan
(INCORPorATe IP3)

NCT: NCT04933812

IRB Document Date: 03/01/2021

EngagINg the COmmunity to Reduce Preterm Birth via Adherence To an Individualized Prematurity Prevention Plan (INCORPorATe IP3): A feasibility study protocol

Introduction:

Non-Hispanic black women are 49% more likely to experience a preterm birth (PTB), delivery before 37 weeks. PTB is associated with increased risk of poor short and long-term neonatal outcomes. PTB can occur in multiple clinical scenarios including spontaneous PTB (e.g. preterm labor, preterm pre-labor rupture of membranes) and medically induced preterm labor (e.g. preeclampsia). Women with a history of PTB are at 1.5 – 2 fold increased risk for future PTB. There are medical therapies that can reduce the risk of recurrent PTB specific to the presumed etiology of the prior PTB. Thus, women with a history of a prior PTB who receive care with Duke Maternal Fetal Medicine (MFM) receive an Individualized Prematurity Prevention Plan (IP3) to reduce their risk of recurrent PTB. The IP3 plans are often labor intensive with requirements ranging from daily medications, weekly clinic visits, painful injections or invasive ultrasounds.

Given the increased rate so of PTB among NHB women and some suggestion of decreased adherence in this population¹, we previously conducted qualitative studies with NHB women to uncover patient perceived barriers to IP3 adherence^{2,3}. These studies revealed that NHB women with prior preterm birth felt that stress and lack of support were key barriers to preterm birth prevention adherence. Stress and limited support made women feel isolated from their peers and community. Based on these data we worked with a stakeholder group to develop a patient-centered, community-involved intervention that will increase adherence to an individualized prematurity prevention plan using community-level social supports. The resulting intervention titled, EngagINg the COmmunity to Reduce Preterm Birth via Adherence To an Individualized Prematurity Prevention Plan (INCORPorATe IP3) includes community doula led group social support.

The primary objective of this protocol is to determine if INCORPorATe IP3 is feasible prior to a larger trial focused on determining efficacy. Feasibility will be measured using the RE-AIM framework⁴: *Reach or Participation (Primary Outcome)*: (a) percent of eligible participants who are successfully recruited and attend at least one group session; *Effectiveness*: retention rate in the intervention; *Implementation*: fidelity to the intervention protocol; *Maintenance*: intervention sustainability based on continued engagement from the participants.

Methods:

Recruitment:

We plan to pilot our intervention with three groups of 5 – 20 women (total up to 60 women). We plan to enroll women who are currently pregnant up to 20 weeks of gestation, who self-identify as non-Hispanic black with a history of prior preterm delivery (before 37 weeks gestation) due to idiopathic preterm labor, preterm pre-labor rupture of membranes, cervical insufficiency or preeclampsia. Further we will include women who are receiving care with the Duke Perinatal Clinics and plan to deliver within

the Duke Health System. We will exclude non-English speaking women, multiple gestation and women with current or prior pregnancy with major fetal anomaly. We will identify participants meeting the eligibility criteria via review of potential participant's electronic medical record. Eligible participants will be approached for enrollment.

Intervention Delivery:

Given limitations of in-person gatherings in light of the COVID 19 pandemic, we developed the intervention to be delivered via virtual platforms. The study protocol will be an adjunct rather than a replacement of traditional prenatal care with Duke Perinatal. The core components of the intervention will be interaction with community doulas and other NHB with prior PTB via facebook group page and group meetings.

After being consented, participants will be given a link to join the private Facebook group. Prior to gaining entry into the private page, participants will be presented with a set of guidelines for appropriate Facebook page usage and must electronically acknowledge receipt and understanding of these guidelines. The Facebook group will include a chat function where group members can respond to questions posed by the doulas and other group members. Participants will be encouraged to interact with one another and ask questions using the chat function on the group page. We also developed a set of discussion prompts to inspire communication and continued community building in between group meetings.

We also plan for eight two-hour long meetings each of which include a pregnancy-related topic and a reflection topic (table 2). The curriculum for the group meetings was designed to address topics salient to the target population while leveraging existing expertise among the community doulas. Group meetings will occur via private zoom meeting link.

Evaluation and Adaptation:

We will solicit feedback from both participants and the doulas throughout the pilot intervention delivery. We will make adaptations to intervention based on the feedback.

Facebook Group

We will solicit feedback from the participants and the community doulas throughout the pilot intervention with the plan to adapt the intervention based on their feedback. Participant feedback on the Facebook group will be derived from engagement metrics that are collected by Facebook. We will assess engagement formally on a monthly basis.

Group Social Support Meetings

We will survey the participants about their satisfaction following each of the eight group meetings. Surveys will be distributed via text messages (Twilio) or email based on the participants preferences. The post-meeting surveys will be brief (approximately 8 questions, see appendix 1) and

focused on participant satisfaction with the length of the meeting and the meeting content. We will also solicit desired topics for future meetings. The study team will compile the survey feedback such that the feedback will remain anonymous.

Outcome Measures:

We will collect basic demographic and pregnancy information based on chart review. Baseline demographics will include age, medical comorbidities, and pregnancy history. During the intervention, we will monitor intervention engagement based on Facebook page engagement, attendance to group meetings and completion of surveys/measures. We will also collect measures of IP3 knowledge, perceived social support, pregnancy specific anxiety and maternal social support using validated scales at three timepoints: intake, after meeting #4, and after the final meeting (#8).

- **IP3 knowledge questionnaire** includes approximately four questions aimed to evaluate a participant's knowledge about the details of their IP3 plan. Participants will only receive questions that pertain to their specific IP3. They will be given the answers immediately following the assessment
- **Pregnancy-Specific Anxiety (PSA):** The PSA is a validated 13-item tool used to assess anxiety specific to pregnancy this tool has been correlated with preterm birth outcome.
- **Interpersonal Processes of Care (IPC):** The IPC is an 18-question questionnaire that asks participants about their experience with receiving care within a specific clinic (in this case the Duke Perinatal Durham Clinic).
- **Maternal Social Support Scale (MSSS):** The MSSS is a six-question scale that quantifies a pregnant woman's social support as low, medium or adequate.
- **IP3 Adherence Data:** We will gather data on adherence to the IP3 based on both participant report and EHR chart review.

We will review the medical record to determine adherence to the IP3 plan and record delivery outcomes (e.g. gestational age at delivery, delivery route, length of hospital stay, etc.)

Selection of Subjects List inclusion/exclusion criteria and how subjects will be identified:

We will recruit 60 pregnant women from the Duke Perinatal Clinics with the following inclusion criteria: self describe race NHB, history of prior singleton preterm delivery (before 37 weeks gestation, current singleton gestation, with IP3 plan. We will exclude women with anomalous fetuses, age below 18 or are non-English speaking. The study staff will approach the subject and provide information regarding the study. If the patient is interested in participating, then study staff will obtain informed consent at that time. The patient can take as much time to decide about participation and the study team will come up with a plan with the patient to follow up on a decision to participate. Voluntariness will be emphasized. Patients will also be told that they were identified as being eligible because their medical chart indicated they have a history of a prior spontaneous preterm birth. For those patients who choose to 'opt out,' to

prevent unwelcome emails, phone calls, or other contacts from those other than a patient's clinician, researchers/study teams must check the opt out status for each patient who may be eligible for their study and exclude those not wishing to be contacted.

Subject Recruitment and Compensation Describe recruitment procedures, including who will introduce the study to potential subjects. Describe how you will ensure that subject selection is equitable and all relevant demographic groups have access to study participation (per 45 CFR 46.111(a) (3)). Include information about approximately how many DUHS subjects will be recruited. If subjects are to be compensated, provide specific prorated amounts to be provided for expenses such as travel and/or lost wages, and/or for inducement to participate.

We will screen clinic schedules and approach women meeting the eligibility criteria during a clinic visit. Consenting participants will be compensated \$20 at intake and \$20 after completion of the exit interview.

There will be three meetings in total.
\$20 for each participant for coming to the meeting and then a raffle of \$200 (which one person will win).
This will happen at all three meetings.

Then there is another 'spot prize' of \$200 which will be raffled for all those that attended the interview – again 1 winner.

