Official Title: EngagINg the COmmunity to Reduce Preterm Birth Via  
Adherence To an Individualized Prematurity Prevention Plan  
(INCORPorATe IP3)

NCT: NCT04933812

IRB Document Date: 01/17/2023

Previous studies have shown preterm births (PTB) are high in non-Hispanic Black (NHB) women and women are more likely to have a PTB if they previously had one. Pregnant women with history of PTB at Duke Maternal Fetal Medicine receive IP3 plans to reduce the risk of recurrent PTB and these interventions are often stressful. The EnagagINg the Community to Reduce Preterm Birth via Adherence To an Individualized Prematuritiy Prevention Plan (INCORPorATe IP3) was developed to provide support for NHB women who had prior PTB. This intervention included information provided through Facebook group discussions with doulas and Zoom group meetings to review a variety of pregnancy-related topics.

Participants received questionnaires to complete at intake, between 20-28 weeks GA, and after 30 weeks GA in addition to group satisfaction surveys after each Zoom meeting. Results from the questionnaires and surveys will be reported as counts (percentages) for categorical variables and mean (SD), median (IQR), and range for continuous variables.

Table 1. Participant Characteristics	
Characteristic	
Age (mean, SD)	
Number of Prior Preterm Births (median, IQR)	
Insurance Status	
Public	
Private	
None	
Body mass index at prenatal care intake (mean, SD)	
Chronic hypertension	
Pre-gestational Diabetes	
Tobacco use at any time in pregnancy	
Preterm Birth Preventative Recommendations (i.e., IP3 plan)	
Lifestyle modifications (n, %)	
Cervix length/Cerclage (n, %)	
Progesterone (n, %)	
Low Dose Aspirin (n, %)	
All data are reported as n (%) unless detailed otherwise	

Table 2. Feasibility and Acceptability Measures	
Recruitment: #Eligible people approach/ # recruited	
Facebook Engagement: Number of participants who logged onto the Facebook page Number of participants who posted/reposted anything Facebook engagement metrics	
Group Social Support (GSS) Session Engagement: Median number of GSS visits attended [IQR] Number (%) of participants who attending 5 or more sessions	

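### The SAP does not tabulate Reach, the primary outcome, and neither document gives an interval or a criterion to support a yes/no finding on feasibility

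*Protocol*

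**What the plan says.** The protocol's Introduction closes with the objective: "The primary objective of this protocol is to determine if INCORPorATe IP3 is feasible prior to a larger trial focused on determining efficacy". Feasibility is to be measured on the RE-AIM framework. The primary outcome is Reach, defined as "percent of eligible participants who are successfully recruited and attend at least one group session". The other dimensions are effectiveness ("retention rate in the intervention"), implementation (fidelity) and maintenance (continued engagement). None of the four has a target value.

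Sample size appears twice. Methods, Recruitment, gives "three groups of 5 – 20 women (total up to 60 women"; Selection of Subjects says "We will recruit 60 pregnant women from the Duke Perinatal Clinics". Both count women recruited. Neither rests on a stated power or precision.

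The SAP's only statement of method covers questionnaires and surveys, whose results are to be "reported as counts (percentages) for categorical variables and mean (SD), median (IQR), and range for continuous variables". The rest is table shells. Recruitment has a row in Tables 2 and 4, given in Table 2 as "Recruitment: #Eligible people approach/ # recruited". Table 2 also asks for the median number of sessions attended and the number attending five or more. Table 3 gives attendance over enrolment, session by session.

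**The concern.** The objective promises a determination, and one outcome is named as primary to inform it. A reader would therefore expect the SAP to compute that outcome, show how precisely it is known, and say how it leads to a conclusion. It does none of these.

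Two things are at stake. First, Reach joins two steps, consent and first attendance. A recruitment fraction reported in its place covers only the first step and can only equal or exceed Reach, because women who consented and never came still count as successes. Second, with no criterion fixed in the documents, a statement that the intervention is or is not feasible would be a judgement made after the result is known. With no interval, the reader cannot see how much uncertainty that judgement carries.

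**Working it through.** **1. The plan's own figure.** The only sample-size figure is 60. It reproduces as 3 groups × 20 women = 60; the lower end is 3 × 5 = 15. No target rate, margin, alpha, power or precision is stated from which 60 could be derived.

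**2. Can Reach be recovered from the SAP tables?** The protocol's definition needs

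Reach = (women recruited who attended at least one session) / (eligible women).

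| SAP row | What it gives | What is missing for Reach |
|---|---|---|
| Tables 2 and 4, recruitment | Approached and recruited (written with approached on top) | The attendance condition |
| Table 2, median sessions attended | Centre and spread of the attendance count | Number with a count of at least one |
| Table 2, five or more sessions | A subset of attenders | Women who attended one to four |
| Table 3, attended/enrolled per session | Attendance at each session | Number of distinct women who ever attended |

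Table 3 gives bounds only. The number who ever attended is at least the largest single-session count and at most the sum of the session counts (or the number enrolled, if smaller), because a woman who comes twice is counted twice. So the numerator is not fixed by any row or combination of rows.

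**3. Is there a criterion anywhere?** The five-session row is the nearest thing to a cut-off. It classifies individual women, has no required proportion attached, and is not Reach. No other threshold, test or interval appears in the SAP, and the protocol adds none.

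**4. How much would an interval matter?** The documents do not give the number of eligible women, n, so it is assumed over a range. It cannot be below the number recruited.
- n = 32: Table 6 of the SAP prints an intake N of 32.
- n = 60: every woman approached is recruited, up to the planned total.
- n = 120: 60 recruited, all attend, and Reach is 50%, so 60 / 0.50 = 120.
- n = 200: a larger denominator, for contrast.

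The Wilson 95% interval at an observed proportion of 0.5 is centred on 0.5, and its half-width simplifies to z / (2√(n + z²)), with z = 1.96 and z² = 3.84:

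| n | Half-width | 95% interval |
|---|---|---|
| 32 | 1.96 / (2√35.84) = 0.164 | 34–66% |
| 60 | 1.96 / (2√63.84) = 0.123 | 38–62% |
| 120 | 1.96 / (2√123.84) = 0.088 | 41–59% |
| 200 | 1.96 / (2√203.84) = 0.069 | 43–57% |

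The half-width runs from about 16 points to about 7. The 50% is itself an assumption; at a given n it is the value that makes the interval widest.

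**The case against.** The strongest reply is that this is a single-arm feasibility pilot, titled as such, which plans to adapt the intervention from feedback as it goes. Such a study can describe feasibility without a pass mark, and a hypothesis test would be out of place. That stands: the absence of a pass/fail rule is not in itself an error. What remains is the mismatch between an objective worded as a determination and a SAP that offers neither a criterion nor an interval.

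Feasibility is also measured on four dimensions, so a rule on Reach alone could pass an intervention that recruits well and retains badly. That stands too, although the other three have no targets either.

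A reader might infer that the pilot formally gates an efficacy trial and so must have a go/no-go threshold on Reach. The documents do not support this. They place the pilot before a larger trial but describe no such trial, timetable or flow of eligible women from which a threshold could be derived.

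Nor is a ready-made rule a safe substitute. Take one that proceeds if the lower limit reaches the threshold, proceeds with changes if only the estimate does, and stops if the upper limit falls below it. With an illustrative 40% threshold and n = 60, it assigns no outcome to 17–23 attenders (28–38%). If true Reach were 35%, the binomial probability of landing there is 64%.

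Finally, timing. The SAP is dated 01/17/2023 and already prints the intake N of 32, so a threshold added then would probably be post hoc. This limits what a criterion could now achieve. It does not affect the table row, the interval or the rewording.

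**Conclusion.** The point holds in a limited form. The SAP as written does not produce the protocol's primary outcome, and nothing in either document turns that outcome into a yes/no answer or shows its precision. The first part rests on the text alone. The size of the second depends on an unknown denominator: at an observed 50%, the 95% interval would span about 33 percentage points with 32 eligible women and about 14 with 200.

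Two further readings go too far. One is that the plan at least delivers a Reach percentage that can be called feasible whatever its value; it delivers a recruitment fraction, which is a different quantity. The other is that 60 is the denominator, so that 38–62% is this trial's precision. Sixty is the planned number recruited; the number of eligible women may be larger and is not stated.

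This is a cheap improvement, not a flaw that undermines the study.

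**What to change.** Add one primary-outcome row to SAP Table 2: Reach = women who consented and attended at least one session / eligible women approached, shown as numerator, denominator, percentage and Wilson 95% confidence interval.

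Reword the objective, and the conclusion drawn from it, as estimating feasibility, unless a progression criterion was set. If one is used, state its value, when it was set, and the outcome for every zone, including an estimate below the threshold with an upper limit above it. Label it post hoc if it was set after Reach data had been seen. The documents give no basis for a particular value, and none is proposed here.

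The cost is one table row and a less definite stated conclusion. The row uses counts of women approached, consented and attending, which the existing table shells and attendance monitoring already call for.

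### The SAP tables count recruitment among women approached and have no row for the protocol's primary outcome, Reach, which is a percentage of all eligible women

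*Protocol*

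**What the plan says.** **Protocol, primary objective (paragraph before Methods).** Reach is labelled the primary outcome and defined as the "percent of eligible participants who are successfully recruited and attend at least one group session". The denominator is eligible women; the numerator requires both recruitment and attendance.

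**Protocol, Methods, Recruitment.** Eligibility is established from the chart: "We will identify participants meeting the eligibility criteria via review of potential participant's electronic medical record". The next sentence states the intention: "Eligible participants will be approached for enrollment". The enrolment window is limited: "We plan to enroll women who are currently pregnant up to 20 weeks of gestation".

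**Protocol, Selection of Subjects.** Staff must check opt-out status for women who may be eligible and "exclude those not wishing to be contacted".

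**Protocol, Subject Recruitment and Compensation.** The setting for first contact is described as follows: "We will screen clinic schedules and approach women meeting the eligibility criteria during a clinic visit".

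**SAP, Table 2.** The recruitment row reads "Recruitment: #Eligible people approach/ # recruited". Table 4 repeats it. The ratio is printed as approached over recruited. No SAP table has a row for women eligible on record review, for eligible women not approached, or for women recruited who came to one or more sessions.

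**The concern.** The protocol and the SAP count from different starting points. The protocol starts from every woman found eligible in the record; the SAP starts from those who were approached. Between the two lie the opt-out exclusion, which is written down, and the practical need to meet the woman at a clinic visit before 20 weeks. A woman who is eligible but not approached for either reason would appear in no SAP count.

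Recruited over approached measures how often women accept when asked. Reach measures how much of the eligible population the programme gets to, and it is the primary feasibility question ahead of a larger trial. If the acceptance rate is read as Reach, a later trial could plan on too high a yield from the same clinics.

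**Working it through.** The documents state no recruitment rate, target rate, number eligible or number approached, so there is no planned figure to reproduce.

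**Inputs**
- Definition of Reach: Protocol, primary objective.
- Recruitment ratio: SAP Tables 2 and 4.
- R = 32, the intake column heading in SAP Table 6. It is used here as a stand-in for the number recruited, which is an assumption, since it heads a questionnaire column.
- A = 40, 50 or 64 approached, and f from 1 down to 0.6: assumed for illustration only.

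**Step 1: the quantities.** Let E be eligible women, A those approached, R those recruited, and S those recruited who came to one or more sessions. Then S ≤ R ≤ A ≤ E. The protocol's outcome is S/E. The SAP row gives A/R, whose inverse is R/A.

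**Step 2: the denominator.** With f = A/E, R/E = (R/A) × f. Hence (R/A) ÷ (R/E) = 1/f.

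**Step 3: the numerator.** With a = S/R, Reach = S/E = (R/A) × f × a. So R/A equals Reach only if f = 1 and a = 1; otherwise it is higher.

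**Step 4: numbers for the denominator alone, R = 32.**

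| f (assumed) | 1/f | R/E if A = 40 | R/E if A = 50 | R/E if A = 64 |
|---|---|---|---|---|
| 1.0 | 1.00 | 80% | 64% | 50% |
| 0.9 | 1.11 | 72% | 57.6% | 45% |
| 0.8 | 1.25 | 64% | 51.2% | 40% |
| 0.7 | 1.43 | 56% | 44.8% | 35% |
| 0.6 | 1.67 | 48% | 38.4% | 30% |

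The first row is also R/A, which does not change with f. Over these values of A, R/A exceeds R/E by 0 points at f = 1, by 5 to 8 points at f = 0.9, and by 20 to 32 points at f = 0.6.

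**Step 5: the ratio as printed.** With A = 40, the SAP row gives 40/32 = 1.25 approached per recruit. At f = 0.8, E = 40/0.8 = 50, and 50/32 = 1.56 eligible per recruit. Inverting the ratio does not change the direction: the approached-based figure is the more favourable one.

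**Step 6: can E or S be found elsewhere in the SAP?** E cannot. For S, Table 2 gives the median number of sessions attended and the number attending 5 or more, and Table 3 gives attendance session by session. Session counts cannot be combined into a count of different women: S lies somewhere between the largest single-session attendance and R. The per-woman attendance counts needed for the median would supply S directly, but no row reports it.

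**The case against.** The strongest reply is the protocol's own sentence: "Eligible participants will be approached for enrollment". If that is carried out, A = E, f = 1 and the two denominators agree. A reader might infer from the recruitment section that women are approached solely at a clinic visit and that eligible women are therefore lost. The documents do not say so. They describe a clinic visit without ruling out other contact, nothing prevents an approach at a later visit, and some prevention plans involve weekly visits. The one written exclusion before contact is the opt-out rule, and neither document settles whether women who opted out count as eligible.

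A reader might also infer that women not approached are the less adherent ones, since the Introduction mentions "some suggestion of decreased adherence in this population". That phrase is no evidence about clinic attendance before enrolment, and neither document has data on it. Non-random loss is a possibility, not a finding.

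Three further replies have weight. Self-identified race and plans to deliver within the health system may need a conversation to confirm, so a denominator of everyone positive on chart review could include ineligible women and understate Reach. Recruited over approached is an ordinary measure, and the SAP labels its row as recruitment, not as Reach. The study is a descriptive single-group pilot with no stated threshold or test, so no stated decision rule changes.

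What remains is that the SAP would not show whether the intention to approach all eligible women was met, and that it provides no row for the primary outcome as the protocol defines it.

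**Conclusion.** The mismatch is real. Followed as written, SAP Tables 2 and 4 yield an acceptance rate among approached women, not Reach. That rate cannot be lower than the eligible-based recruitment rate, and it exceeds it by the factor 1/f as soon as one eligible woman is not approached. The requirement to attend a session can only lower Reach further.

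The size cannot be determined from the documents. The gap is zero if f = 1; the factors 1.11 to 1.67 rest on assumed values of f from 0.9 to 0.6, and the percentages also on assumed A and on 32 as the number recruited. The documents do not support the stronger statement that recruitment will in fact look better than it is. The point should be corrected because it concerns the primary outcome and the remedy is small.

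**What to change.** In SAP Tables 2 and 4, replace the single ratio with counts for:

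1. eligible on record review, with women whose eligibility the record cannot settle shown separately;
2. opted out of contact;
3. not approached, with reasons where records allow;
4. approached;
5. found ineligible on contact;
6. consented;
7. attended one or more sessions.

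Report Reach as women in line 7 over eligible women, leaving out those found ineligible on contact, once with and once without the opt-outs. Show recruited over approached, printed that way up, as a secondary acceptance rate.

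If the counts before approach cannot be recovered, label the SAP figure an acceptance rate among approached women and state that Reach could not be computed. This may arise: neither document specifies a screening log, and the SAP, dated 01/17/2023, already shows 32 women at intake.

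The cost is extra tabulation and a percentage that may be less favourable. Nothing in study conduct or care changes.
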